We will use The Patient Feedback Questionnaire (PFQ). The questionnaire was used in a previous study which evaluates the efficacy of an iCBT program for panic attacks and it was developed by a team of researchers (Ciuca et al., 2011). The questionnaire contains 14 items which evaluate the patients' satisfaction with the platform and several other aspects (quality and utility of different components of the platform). Other items refer to giving improvement suggestions, what they like most, if they would use it again or recommend it to a friend with symptoms related to traumatic experiences. The questionnaire will be administered at post-treatment evaluation.

Drop-out reasons

In order to evaluate the reasons for drop-out we will use a questionnaire developed by Ciuca et al. The questionnaire contains 18 items and each item is considered to be a possible reason (e.g. lack of motivation, lack of time, different expectations, exacerbation of symptoms, interface is too complicated, the treatment pace is too slow or too fast, finding another treatment, getting better, important life events etc.) (Ciuca et al., 2011).

Side effects

We will evaluate negative side effects after completion of the intervention to identify any negative effects of PAXPTSD program. For this at the end of the program, participants will complete the Positive and Negative Effects of Psychotherapy Scale (PANEPS) (Moritz et al., 2018). PANEPS was evaluated in a population of individuals with depression who had completed at least one course of face-to-face psychotherapy. Factor analysis yielded four dimensions: positive effects, side effects, malpractice, and unethical conduct. Internal consistency of PANEPS range between 0.72 - 0.92 (Herzong, Lauff, Rief & Brakemeier, 2019).

Randomization

Participants who return the informed consent and meet all the required criteria are randomly allocated to one of the two conditions . The randomization process is done by a software that was developed to implement a minimization algorithm (Pocock & Simon, 1975) that assures a balanced randomization between groups with respect to certain predefined prognostic (stratification) factors. In this study, two stratification factors have been considered:

SEVERITY(4 levels according to PDS-5 screening scores; level 1: 11 to 23 points; level 2: 24 to 42 points; level 3:

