43 to 59 point; level 4: 60-80) and CHRONICITY (2 levels; more or less than 3 months since the traumatic event). The minimization method has been shown to outperform simple randomization in achieving balanced groups (Scott, McPherson, Ramsay, & Campbell, 2002) and its use in clinical trials has been previously recommended as a better option than other randomization methods (Hagino et al., 2004; Scott, McPherson, Ramsay, & Campbell, 2002; Treasure & MacRae, 1998). Before each allocation, the algorithm computes an imbalance score for the two available treatments, taking stratification factors levels into account. The treatment with the lowest imbalance score is then given preference when assigning treatments, but the allocation probability varies for each patient, depending on the actual level of imbalance (Hofmeijer, Anema & van der Tweel, 2008). This method is preferred because it avoids the deterministic allocation of pure minimization (Pond, 2011). The allocation is done by an independent researcher and is concealed, i.e. patients and researchers have no knowledge and no control over the allocation of participants when they randomize a participant with the computer program.

Blinding

Taking into consideration the characteristics of our research it is impossible to keep patients blind to the study procedures and psychotherapists' intervention. All participants are provided with detailed information about the aims and the methodology of the study. They can request more information about the study and they have the right to terminate participation at any time. The personnel in charge of the clinical interviews will be blind to the treatment group allocation. We specifically instruct the participants not to mention group allocation at the post-assessment interview, but also test whether blinding was successful. The clinicians who conduct the diagnostic interviews are required to describe in their report if their participants disclosed their study group, directly or indirectly (Ciuca et al., 2011; Weisel et al., 2018).

Sample size

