The effect size for iCBT intervention for PTSD is considered to be small to medium (Kuester, Niemeyer & Knaevelsrud, 2016; Lewis et al., 2019; Sibrandij, Kunovski & Cuijpers). Take this information in consideration we expected an effect size of .60. Based on this effect size, a power of .80 and a level alpha of 0.05 we would need 45 participants in each condition for testing the two tails hypothesis. This recommended sample size has been increased to accommodate an attrition rate of 20%. Thus, the study aims to achieve a total sample of 108.

Statistical analysis

All statistical analyses will be performed using the IBM SPSS Statistics version 20. The aim analysis will be conducted on intention-to-treat samples. We will use a linear mixed effects models approach with full information maximum likelihood estimation. This approach was recommended since it uses all available data and can handle missing data appropriately (Gueorguieva & Krystal, 2004; Meyer et al., 2015; Pond, 2011). The approach emphasizes the assumption that data are randomly missing and does not assume that missing data remain stable as in the last-observation-carried-forward (LOCF) approach (Blankers, Koeter & Schippers, 2010; Meyer et al., 2015). Significance testing of dichotomous data such as diagnostic status will be conducted with chi-square tests. Calculation of within and between- groups effect sizes (Cohen d) will be based on the pooled standard deviations. Regression analyses will be used to identify predictors of treatment outcome. Moderation and mediation analysis will be conducted with multiple regression models, using the PROCESS macro for SPSS (Hayes, 2017), a computational technique that can compute both simple and complex moderation and mediation models. Effect sizes for significant effects will be indicated by Cohen's d.

Consistent with recommendations from CONSORT (Schulz, Altman, Moher, 2011) and SPIRIT (Chan et al., 2013) we mention our intention to perform secondary analyses for minimal treatment users, defined as participants that complete at least 5 of recommended modules and use the intervention program for at least 80 minutes. This definition is based on the specific of our intervention program and the criteria used in other studies (Ciuca et al., 2011; Meyer et al., 2015; Ivarsson et al., 2014).

Discussion

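### Allocation is minimised on two prognostic factors, but diagnostic status is tested by a plain chi-square that ignores both: valid, but conservative if the factors predict diagnosis

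*Protocol*

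**What the plan says.** In the Randomization section, allocation uses a minimisation algorithm with a random element, meant to balance the arms on factors the protocol itself describes as prognostic: "two stratification factors have been considered". The first is severity, in four bands of the screening PDS-5 score (11–23, 24–42, 43–59, 60–80). The second is "CHRONICITY (2 levels; more or less than 3 months since the traumatic event".

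For binary outcomes the Statistical analysis section says: "Significance testing of dichotomous data such as diagnostic status will be conducted with chi-square tests". No stratified or covariate-adjusted version is given. Regression is mentioned in that section, but for predictors of outcome, moderation and mediation, not for the comparison of arms on diagnosis.

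The Diagnostic interview section adds that a missing post-treatment diagnosis is counted as PTSD still present.

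**The concern.** Design and analysis do not match for this endpoint. Once the arms are forced to be alike on severity and chronicity, those factors can contribute little to a chance difference between arms. A two-by-two chi-square does not know this. Its variance includes the spread in diagnosis rates across severity and chronicity levels, so its standard error is too large whenever those levels predict diagnosis.

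The result is a test that rejects less often than its nominal 5% and has less power than the design allows. Diagnosis comes from interviewers blind to allocation, in a trial whose participants cannot be blinded, so it is an endpoint on which lost sensitivity matters. This is a stated choice of test, not an omission that an analysis plan would be expected to fill.

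**Working it through.** **The protocol's own figure.** A standardised difference of 0.60, two-sided alpha 0.05 and power 0.80 give 44.6, so 45 per arm, by the two-sample t-test. Then 45 × 1.2 = 54 per arm and 2 × 54 = 108. The stated figures reproduce. They concern a continuous outcome with no covariate adjustment; no power is claimed for diagnostic status.

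**Inputs.** From the protocol: N = 108, two factors with four and two levels, non-deterministic minimisation, chi-square test. Assumed, because the documents do not give them:
- severity bands hold 10%, 40%, 35% and 15% of participants, and 85% fall in one chronicity level;
- the preferred arm is assigned with probability 0.8 (the protocol lets this probability vary with imbalance);
- the log-odds of still having PTSD are 1.0 in the control arm at average factor values, and treatment changes them by −1.2. That is 1/(1+e^−1.0) = 73% against 1/(1+e^0.2) = 45%.

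The missing-equals-PTSD rule is not built in. If missingness is unrelated to the factors, that rule would usually weaken their association with the outcome.

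**Step 1: the mechanism by hand.** With perfect balance, the chi-square variance is too large by the share R = (between-level variance of the diagnosis rate) / p̄(1−p̄). The actual type I error is then P(|Z| > 1.96/√(1−R)). For severity alone, with log-odds 1.2 per level and no treatment effect:
- rates by level are 0.297, 0.584, 0.823 and 0.939, so p̄ = 0.6925 and p̄(1−p̄) = 0.2129;
- between-level variance is 0.0355, so R = 0.0355/0.2129 ≈ 0.166;
- 1.96/√0.834 ≈ 2.147, giving a type I error of about 3.2%.

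The same sum gives about 4.1% at 0.8 per level and 4.7% at 0.4 per level.

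**Step 2: simulation.** There were 4,000 trials per cell. The plain chi-square was compared with a likelihood-ratio test from logistic regression on arm, severity level and chronicity.

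| Log-odds per severity level / chronicity | Chi-square type I | Adjusted type I | Chi-square power | Adjusted power | Gap | Gap less 1.2 |
|---|---|---|---|---|---|---|
| 0 / 0 | 5.1% | 5.4% | 84.65% | 85.83% | 1.2 | 0 |
| 0.4 / 0.5 | 4.9% | 5.8% | 82.50% | 84.48% | 2.0 | 0.8 |
| 0.8 / 0.8 | 3.8% | 5.4% | 77.55% | 81.85% | 4.3 | 3.1 |
| 1.2 / 1.0 | 3.4% | 5.4% | 68.40% | 77.85% | 9.4 | 8.3 |

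The last column removes the 1.2-point gap seen with no prognostic effect, which reflects the slightly larger size of the adjusted test rather than any gain in precision. Monte Carlo standard error is √(0.05 × 0.95/4000) = 0.34 points for type I error and about 0.6 to 0.7 points for power. The fall to 3.8% and 3.4% is therefore not noise, and it agrees with step 1.

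**Step 3: cross-check.** A second simulation, with its own assumed intercept and chronicity effect, ran 3,000 trials per cell with treatment log-odds 1.2 and the same 0.8 probability. It set severity at 0, 0.3, 0.5, 0.7 and 1.0 log-odds per standard deviation. Power, chi-square against adjusted, was 83.6/83.7, 81.6/82.1, 80.2/81.7, 76.9/79.3 and 70.9/76.3, so the gaps are 0.1, 0.5, 1.5, 2.4 and 5.4 points. Chi-square type I error stayed at 4.7–5.3% up to 0.7 per standard deviation.

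To compare scales: the assumed bands have variance 3.15 − 1.55² = 0.7475 and standard deviation 0.865. So 0.4, 0.8 and 1.2 per level are about 0.35, 0.69 and 1.04 per standard deviation. Near 0.7 the two simulations give 3.1 and 2.4 points; near 1.0 they give 8.3 and 5.4.

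**The case against.** The strongest reply is that nothing here is invalid. The chi-square does not inflate false positives, the treatment comparison is not biased, and the balance from minimisation is kept. If the factors predict diagnosis only weakly, the loss is about zero, and the documents give no evidence of a strong association. The adjusted test is not free either: it ran at 5.4–5.8% type I error in the first simulation, and logistic regression targets a conditional odds ratio, so a marginal risk difference needs an extra step. All of this stands. It limits the size of the point but does not make the plain chi-square the better main test.

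Two stronger readings are tempting and are not supported.

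- A reader might infer that the continuous analysis also ignores the factors. The protocol says only "We will use a linear mixed effects models approach with full information maximum likelihood estimation" and lists no model terms at all, not even arm or time. Such terms are commonly left to an analysis plan, so this is silence, not a decision. The gain would also be small. Pre-treatment PDS-5 is already measured; if it correlates 0.5 with the outcome and is used, residual variance is 0.75, and adding both factors lowers it only to about 0.70–0.73.
- A reader might infer that the trial's stated power is eroded. That power rests on "we expected an effect size of .60", a standardised difference for a continuous comparison without adjustment. A loss on diagnostic status leaves it untouched.

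**Conclusion.** The point holds for diagnostic status only. The protocol balances allocation on factors it calls prognostic and then names a test that cannot use them. The test is valid but conservative when those factors predict diagnosis.

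Under the illustrative assumptions, type I error falls from about 5% to as low as about 3.4%. The power loss is about 0 to 1.5 points for a weak association, roughly 2 to 5 for a moderate one and up to about 8 for the strongest one tried. These figures depend on assumed diagnosis rates, factor distributions and associations that the documents do not supply. The direction does not depend on them; the size does. This is a worthwhile gain in efficiency, not a threat to the validity of the result.

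**What to change.** In the Statistical analysis section, state that the main between-arm test of post-treatment diagnostic status is a logistic regression on arm, screening PDS-5 score (continuous) and chronicity (two levels). A Cochran-Mantel-Haenszel test stratified by the minimisation factors is an acceptable alternative. Keep the existing rule that a missing diagnosis counts as PTSD still present. Report a marginal (standardised) risk difference with its 95% confidence interval, and keep the chi-square as a supportive analysis.

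Both variables are already needed to run the allocation, so no new data are collected. The costs are slightly more analysis work, wording that separates the conditional odds ratio from the marginal effect, and a small-sample check of type I error before the test is fixed, given the 5.4–5.8% seen for the likelihood-ratio version.
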